The retrospective part of the I³LUNG project includes the analysis of a multicentric retrospective cohort of more than 2,000 patients. This cohort will be used to perform a preliminary knowledge extraction phase and to build a retrospective predictive model for IO (R-Model), that will be used in the prospective study phase to create a first version of the Physician Decision Support System (PDSS) tool, an AI-based tool to provide an easy and ready-to-use access to predictive models, increasing care appropriateness, reducing the negative impacts of prolonged and toxic treatments on wellbeing and

	
healthcare costs. Also, CT and PET scans will be collected and a first radiomic signature will be created to feed the R-Model.
 
The prospective part of the project includes the collection and the analysis of multi-OMICs data from a multicentric prospective cohort of about 200 patients. This cohort will be used to validate the results obtained from the retrospective model through the creation of a new model (P-Model), which will be used to create the final Physician Decision Support System (PDSS) tool.

	
Overall Primary Objective

	
 • Prediction of response to immune checkpoint inhibitors in NSCLC by using clinical, biological, metabolomics, genomics, pathomics and radiomics data.
	
Secondary Objectives

	
 • Prediction of Progression-free survival (PFS) in response to immune checkpoint inhibitors in NSCLC by using clinical, biological, metabolomics, genomics, circulomics, pathomics, microbiome and radiomics data.
	
 • Prediction of Objective Response Rate (ORR) in response to immune checkpoint inhibitors in NSCLC by using clinical, biological, metabolomics, genomics, circulomics, pathomics, microbiome and radiomics data.
	
 • Prediction of Overall survival (OS) in response to immune checkpoint inhibitors in NSCLC by using clinical, biological, metabolomics, genomics, circulomics, pathomics, microbiome and radiomics data.
	
Exploratory Objectives

	
 • Added value of PET/CT into the prediction model for the Primary and Secondary Objectives.
	
 • Prediction of adverse events to immune checkpoint inhibitors in NSCLC by using clinical, biological, genomics, pathomics and radiomics data.

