Study Endpoints	
Primary endpoint
 
 The predictive model will be developed through artificial intelligence and machine learning analysis of the integrated clinical, biological, genomics, metabolomics, circulomics, pathomics, microbiome and radiomics data. 
Secondary endpoints
 
 Using the predictive model index as classificatory biomarker in Progression-free survival (PFS), defined as the time interval from the date of the first dose of the study treatment until the first date at which disease progression is objectively documented, or death due to any cause, whichever occurs first and calculated through censored Kaplan-Meier analysis. Prediction of Objective response rate (ORR) classification through the predictive model and compared to the assessed by the investigator and defined as the proportion of the participants with confirmed complete response (CR) or partial response (PR) according to Response Evaluation Criteria in Solid tumors (RECIST) v1.1, after initiation of immune checkpoint inhibitors treatment. Using the predictive model index as classificatory biomarker in Overall survival (OS) calculated from diagnosis to death or last follow-up through censored Kaplan-Meier analysis. 
Exploratory endpoints
 
 If available PET/CT will be added to the prediction model and the increment in the prediction performance will be analyzed for the primary and secondary endpoints and the adverse events categories. Machine learning algorithm will be used to predict adverse events categories in response to immune checkpoint inhibitors treatment through the integration of the clinical, biological, genomic, pathomics and radiomics. 
Sarcopenia will be calculated through radiomics by measuring the fat and muscular mass on L1 slice of the chest CT scan and added to the prediction model for the Primary and Secondary Objectives.

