	
RETROSPECTIVE PHASE:
 
The study cohort consists of aNSCLC patients treated with IO. Data from an estimated 2000 patients treated with IO-based therapy (any treatment line) in the period 2012-2021 will be collected from all the clinical partners (INT, GHD, VHI, MH, SZMC and UOC). Inclusion criteria will be checked and informed consent for the study and for the re-use of prior collected medical data will be obtained before enrolment. If not feasible, i.e. patients not alive, the approval to Privacy Guarantee will be obtained.

	
Inclusion criteria retrospective phase:
 
 1. Age \geq 18 years 2. Presence of an Eastern Cooperative Oncology Group (ECOG) performance status \leq 2; 3. Histologically confirmed diagnosis of stage III-IV Non-Small-Cell Lung Cancer patients receiving also maintenance therapy with durvalumab or other immune/combination are allowed; 4. Patients who received any line of IO-based therapy (immunotherapy monotherapy or immunotherapy in combination with any other treatments); 5. Patients with any CNS mets (stable or not) are allowed.

		OBSERVATIONAL STUDY PROTOCOL	MOD-PRO-G-03- DSC-10
--	---	---	---------------------------------

6. Patients with driver alteration (e.g., EGFR, BRAF, KRAS mutations or ALK, ROS1) who underwent an immunotherapy line will be included.

Exclusion criteria retrospective phase:

1. Patients without minimal treatment information data (e.g. start and stop date of immunotherapy and type of immunotherapy agent or protocol name)

PROSPECTIVE PHASE:

In the prospective phase, the study cohort consists of aNSCLC patients candidate for first-line IO-based therapy with available surgical samples (enough to perform OMICs). Baseline data of an estimated 200 patients from 5 clinical centers (INT, GHD, VHIO, MH and SZMC) will be collected including complete clinical, multi- OMICs analysis, imaging of CT and PET scan at baseline IO, behavioral, health economic, QoL measurements with based-sensor techniques and standard QoL. Data treated with IO-based therapy (any treatment line) will be collected. Inclusion criteria will be checked and informed consent for the study and for the re-use of prior collected medical data will be obtained before enrolment.

Inclusion criteria for prospective phase:

1. Age ≥ 18 years.
2. Evidence of a personally signed and dated ICF indicating that the patient has been informed of and understands all pertinent aspects of the study before enrolment.

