3. Eastern Cooperative Oncology Group (ECOG) performance status " 0-2.
4. Histologically confirmed diagnosis of stage IIIB/C-IV Non-Small-Cell Lung Cancer
5. No activating EGFR mutations or ALK/ROS1 rearrangements
6. No prior treatment for advanced disease
7. Availability of at least 1 (one) FFPE block for -omics data generation (for cohort 200 pts)
8. Clinical indication for frontline treatment with immunotherapy (alone or in combination), as first line of treatment for metastatic disease or consolidation treatment for locally advanced disease
9. Patients with untreated or unstable CNS brain metastases are allowed

Exclusion criteria for prospective phase:

1. Prior systemic treatment for NSCLC for advanced disease
2. Absence of sufficient amount of tumor tissue for -omics data generation for OMIC cohort (200 pts).
3. Unavailability or inability to comply with the requested study procedures, including compilation of QoL questionnaires and behavioral data collection (mobile app).
4. Unable to participate in the psychological study

	
Data for -omics analysis from patients considered screening-failure and, therefore, not eligible for the prospective phase of the protocol, will also be collected to feed the AI models using their real-world data generated during IO-based treatments. There is no limit for sample size in this phase and are not counted within the 200 patients who will be eligible for the multi-OMICs analysis.
																				
	
Scientific Clinical Study Design
 
I³LUNG will conduct an observational retrospective/prospective multicenter international project on advanced Non-Small-Cell Lung Cancer patients treated with IO. Its main objective is to study, train and validate the predictive accuracy of ML methods created by using real world data and multi-OMICs analyses, compared to the current standard of care biomarkers (e.g., the PD-L1).
 
The prospective study part of the project will start at month 3 and will continue up to 36 months, NSCLC patients candidates (n=200) to first-line IO-based therapy with available surgical samples (enough to perform -omics) will be enrolled.
 
In particular, will be collected the following data for Retrospective Phase (when available) and for Prospective phase:
																				

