Demographic characteristics (age, gender, height, body weight, ethnicity, family history of cancer, Smoking History, asbestos exposure, alcohol consumption, drug use history).	✓	✓																			
Medical history (personal medical history of cancer and other severe chronic diseases, allergies and concomitant medications)	✓	✓																			
Health-economic details (site of treatment administration, lost workdays, etc.)	If available	✓																			
Lifestyle factors (diet and use of supplements, physical activity, daily heart rate, sleep patterns, QoL)		✓																			
Clinical findings: 
 - Performance Status (ECOG), Vital signs (blood pressure, oxygen saturation, (BP, SpO2), Temp, breaths/min, pulse). - Main symptoms leading to diagnosis, main symptoms at initiation of immunotherapy. Presence of main disease-related symptoms (shortness of breath, cough, pain and fatigue). 	✓	✓																			

 
Sistema Socio Sanitario Regione Lombardia
		OBSERVATIONAL STUDY PROTOCOL	MOD-PRO-G-03- DSC-10
---	---	---	---------------------------------

	
 - Body weight/height/BMI/BSA and weight loss prior to diagnosis and prior to initiation of IO (kg/months). - Major findings at clinical examination at diagnosis. 		
	Laboratory findings: Hb, WBC, Neutrophils, Lymphocytes, NLR (neutrophil/lymphocyte ratio) at IO initiation and post-treatment change in NLR, Platelets, Albumin, LDH, Ferritin, Creatinine, Creatinine clearance, Na, ALP, Glucose, CRP.	✓	✓
	Tumor characteristics: Histology, Grade, Ki 67, mutational status (e.g. EGFR, BRAF KRAS, ALK, ROS1) and PD-L1 expression, TNM stage, Sites/organs of metastases. Time from initial diagnosis to first metastatic disease.	✓	✓
	Treatment Characteristics: 
 - previous treatments, previous platinum use and response, - 1st line treatment combination (IO vs CT+IO or other IO combinations). - Regimen duration, number of cycles, details of maintenance treatment. Best response to 1st line. Duration of response, PFS, OS. - Toxicity details (type of toxicity, grade). Use of supportive medication (growth factors, anti-emetics). 	✓	✓
	Radiomics	✓ (CT +PET, the later when available)	✓ (CT + PET scan)
	Immunohistochemistry data (e.g., CD3, CD4, CD8, CD20, CD11c, CD68, PD-1, PD-L1 and TIGIT)		✓
	Citomic: Immune phenotype and single cell analysis of circulating populations (i.e. PBMCs, PMNs)		✓

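### Overall survival is counted from diagnosis although patients enter by having received immunotherapy, so the any-line retrospective cohort is credited with guaranteed survival time

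*Protocol*

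**What the plan says.** In the protocol's Study Endpoints, the OS endpoint uses the model index as a classifying biomarker for "Overall survival (OS) calculated from diagnosis to death or last follow-up through censored Kaplan-Meier analysis". The PFS endpoint two items above uses a different clock, the "time interval from the date of the first dose of the study treatment". The matching item under Secondary Objectives is "Prediction of Overall survival (OS) in response to immune checkpoint inhibitors in NSCLC".

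The retrospective inclusion criteria admit "Patients who received any line of IO-based therapy", for about 2000 patients treated in 2012-2021. Patients lacking minimal treatment data, for example "start and stop date of immunotherapy and type of immunotherapy agent", are excluded. The prospective criteria require "No prior treatment for advanced disease", but also allow IO as consolidation for locally advanced disease.

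The baseline data table collects, for both phases, "Time from initial diagnosis to first metastatic disease" and "previous treatments, previous platinum use and response". The protocol does not say whether the OS clock starts at the initial diagnosis or at the diagnosis of advanced disease. It nowhere mentions delayed entry, left truncation, a landmark, or OS from IO start.

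**The concern.** A patient who died after diagnosis but before IO cannot be in the retrospective cohort. The interval from diagnosis to IO start is therefore survived by design. An estimator that handles only censoring treats every patient as at risk of death throughout it. The origin also misses the objective, which concerns survival in response to checkpoint inhibitors.

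Two consequences follow for the retrospective cohort:

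- The OS curve is too high, by an amount that grows with the delay and so with the line of treatment.
- A model index that tracks the delay looks prognostic for OS with no relation to survival after IO. Previous treatments, and time to first metastasis if the clock starts at initial diagnosis, could carry this information if used as features. The protocol does not list the final features, so this second consequence is conditional.

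The retrospective model feeds the first version of the physician decision tool. The success rule in the AI analysis plan uses 2-year OS in the prospective cohort, where the distortion depends on how many patients have a long interval since diagnosis. Response and PFS are not affected.

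**Working it through.** The protocol states no delay and no survival figure, so there is nothing of its own to reproduce. The figures below show the size under assumed inputs.

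**Model.** The delay D from diagnosis to IO follows a gamma distribution with shape 2 and mean m. Survival T after IO is exponential with median M and independent of D. OS from diagnosis is D + T. With β = 2/m, λ = ln 2/M, a = β − λ and t = 24 months,

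P(D + T > t) = e^(−βt)(1 + βt) + β² e^(−λt) [1 − e^(−at)(1 + at)] / a².

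From IO start the 2-year OS is 2^(−24/M), which is 25% for M = 12.

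**Example, M = 12, m = 12.** β = 0.1667, λ = 0.0578, a = 0.1089. The first term is e^(−4) × 5 = 0.092. The second is 0.586 × 0.735 = 0.430. The sum is 0.522.

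**1. Retrospective, same survival after IO in every line (M = 12).**

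| Group | Mean delay, months | 2-year OS from diagnosis | 2-year OS from IO start |
|---|---|---|---|
| First line | 1.5 | 27% | 25% |
| Later line | 8 | 42% | 25% |
| Later line | 10 | 47% | 25% |
| Later line | 12 | 52% | 25% |

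The AUC of a yes/no marker is 0.5 + 0.5 × (share of later-line among 2-year survivors − share among non-survivors). With half the cohort later-line at mean delay 12, these shares are 0.261/0.398 = 0.656 and 0.239/0.602 = 0.397, so the AUC is 0.63. With 30-50% later-line and mean delays of 8-12 months the range is 0.57-0.63. With M = 18 it is 0.56-0.61. From IO start it is 0.50 throughout.

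**2. Retrospective, later-line patients truly worse (M = 9 against 15).** From IO start, 2-year OS is 16% later-line and 33% first-line. From diagnosis:

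| Later-line mean delay, months | Later line | First line |
|---|---|---|
| 8 | 32% | 35% |
| 10 | 38% | 35% |
| 12 | 44% | 35% |

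The true gap of 17 points nearly vanishes at 8 months and is reversed at 10 and 12.

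**3. A different model, with survival measured from diagnosis as the target.** Survival from diagnosis is exponential with median 12 months (true 2-year OS 25.0%), and patients enter only if alive at IO start.

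| Delay | Ordinary Kaplan-Meier, 2-year OS | With entry at IO start |
|---|---|---|
| First line, mean 1.5 months | 27.2% | 25.1% |
| Half first line, half mean 9 months | 32.4% | 24.9% |
| Later line, mean 12 months | 46.3% | 25.5% |

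In the mixed cohort a later-line marker with no effect on the hazard has Harrell's C of about 0.58 from diagnosis and 0.50 from IO start.

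**4. Prospective (model of steps 1 and 2, M = 12, true 25%).** Where a range is given, the lower value is for the group indicator and the upper for the delay itself. The all-prompt row is for the delay.

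| Assumed mix | 2-year OS from diagnosis | AUC | C to 24 months |
|---|---|---|---|
| All prompt, mean 1.5 months | 27% | 0.52 | 0.53 |
| 20% consolidation, mean 5 months | 29% | 0.53-0.55 | 0.53-0.56 |
| 10% with mean 18 months since first diagnosis | 31% | 0.58-0.60 | 0.55-0.58 |
| 20% with mean 18 months | 35% | 0.63-0.66 | 0.59-0.62 |

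**The case against.** **The OS endpoint may be meant for the prospective cohort only.** Most omics layers of the model are collected only there, and no separate retrospective OS test is set out. This does not hold: the objectives are headed as overall ones, OS is among the data collected retrospectively, and the image-analysis section fits a Cox survival model developed on the first 1000 images and validated in about 1000 remaining patients. Those numbers can only be the retrospective cohort.

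**The success rule is prospective, and there the effect is small.** This stands for patients who start IO promptly. The larger prospective figures need 10-20% of patients with long intervals since first diagnosis. The protocol allows surgical tissue, so such patients are possible, but it gives no share. If the clock starts at advanced diagnosis, those scenarios disappear.

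**An index unrelated to the delay is barely affected.** This also stands. In a simulation with assumed prospective inputs, such an index had C of 0.677 from either origin when all start promptly. With 10% at 18 months it had 0.676 from IO start and 0.668 from diagnosis. The AUCs above are for line or delay alone, not for the planned multi-source index.

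**Survival from diagnosis is a different quantity, not a biased one.** This is partly fair for the first model, where some of the gap is the change of origin. The third step answers it: with survival from diagnosis as the target, ordinary Kaplan-Meier still gives 46.3% against a true 25.0%.

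**No comparison of lines is planned.** This is correct, since line is not a listed stratification factor. The reversed ranking illustrates the distortion and is not a planned result.

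**The analysis plan could add delayed entry.** It could, but the protocol itself fixes the origin and names censoring only, so this is a stated choice and not a detail left open.

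**Conclusion.** The concern holds. As written, OS in the any-line retrospective cohort counts survival guaranteed by the entry criterion as time at risk. The direction is certain: OS is overstated, most for later-line patients. The size depends on assumed delays and survival. With post-IO medians of 12 or 18 months and later-line delays averaging 8-12 months, line of treatment alone reaches an AUC of 0.56-0.63 with no true effect; the study is sized to detect an AUC gain of 0.1. Whether the model picks this up depends on features the protocol does not list.

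In the prospective cohort, and so for the 2-year OS success rule, the effect is small unless a notable share of patients have a long interval since diagnosis. This is a secondary endpoint and should be fixed; the response and PFS analyses stand.

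**What to change.** In Study Endpoints, define OS in both phases from the date of the first dose of the IO-based treatment, as for PFS. Use that definition for the Kaplan-Meier curves, the 2-year OS outcome and the C statistic. If OS from diagnosis is also reported, state whether initial or advanced diagnosis is meant and let patients enter the risk set at IO start (left truncation).

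The cost is one sentence. The IO start date already belongs to the minimal data for retrospective entry and is needed for PFS, so nothing new is collected. The drawback is that OS figures will be less favourable and less comparable with series that count from diagnosis.

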Background and Rationale	
BACKGROUND
 
Lung cancer is the leading cause of cancer-related mortality worldwide. The global incidence in 2020 was an estimated 2.2 million cases with an estimated 1.8 million deaths. A 70% increase in the number of new cases of lung malignancy is expected over the next 2 decades (1). There are two major families of lung cancers: small cell lung cancer (SCLC), which accounts for approximately 15-20% of total cases, and non-small cell lung cancer (NSCLC), which accounts for approximately 80-85% (2). About 70% of patients with NSCLC, at the time of diagnosis, have advanced disease not amenable to surgical resection while SCLC is always considered a systemic disease (3). For several decades, cytotoxic chemotherapy has been the only treatment able to prolong survival in advanced patients with both SCLC and NSCLC. In recent years, in NSCLC, progress in cell biology have led to the identification of specific genetic alterations, known as "driver" alterations, at the basis of tumorigenesis, including mutations of EGFR, KRAS and BRAF and rearrangements of ALK, ROS1, RET genes. The use of "target therapies" is now the treatment choice in this subgroup of patients (4-11). The advent of immunotherapy has further changed the therapeutic landscape in both NSCLC without "driver" alteration (NSCLC-WT) and SCLC. This is a treatment modality based on mobilization of the immune system in order to recognize and destroy tumor cells. Immune Checkpoint Inhibitors (ICIs), have been developed with the intent to act on those pathways of "self-tolerance" used by tumors to escape recognition and destruction by the immune system. By blocking these inhibitory pathways, which physiologically control the immune response, ICIs reactivate and sustain the immune system response against tumors cells (12). Cytotoxic T-lymphocyte-associated-4 (CTLA-4) and programmed cell death protein 1 (PD-1) are receptors expressed on T cells that, by interacting with CD80/CD86 (13) and programmed cell death protein 1 (PD-L1) or PD-L2 ligands, respectively (14), can promote and foster immune evasion by tumor cells. PD-L1 evaluation on tumor remains the only used and approved predictor of response to immunotherapy (IO) treatment. Although the probability that a patient will benefit from IO treatment is higher in high PD-L1 expression, the role of PD-L1 remains unclear as a predictive role (15-20).
 
As a general guideline, the lack of alterations in target genes and PD-L1 expression > 50% allow to candidate a patient for first-line treatment, single-agent IO or its combination with chemotherapy based on platinum regimen (CHT). In patients with PD-L1 expression 1-49%, IO alone showed modest activity, while the CHT-IO therapy demonstrated to significantly prolong patient survival compared to CHT alone, in both squamous and non-squamous NSCLC (10).
 
To date, FDA and EMA approved for use in advanced NSCLC patients of nivolumab and pembrolizumab (antibodies against PD-1), and atezolizumab and durvalumab (antibodies against PD-L1). Due to the better efficacy and safety profile compared with chemotherapy, pembrolizumab, nivolumab, and atezolizumab were approved as monotherapies, pembrolizumab as first and second line treatment, whereas nivolumab and atezolizumab only in second line (15-19). Durvalumab is

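### The retrospective data table collects best response for first line only, although that cohort received immunotherapy (IO) in any line, so later-line IO patients have no field for the response that the ORR endpoint needs

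*Protocol*

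**What the plan says.** All references are to the protocol.

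- **Retrospective population.** The cohort is about 2000 patients "treated with IO-based therapy (any treatment line) in the period 2012-2021". Retrospective inclusion criterion 4 repeats this: "Patients who received any line of IO-based therapy".
- **What is collected.** The Treatment Characteristics row of the data table under Methodology and study design is ticked for both phases. It lists, in order, "previous treatments, previous platinum use and response"; then "1st line treatment combination (IO vs CT+IO or other IO combinations"; then regimen duration and cycles, followed by "Best response to 1st line. Duration of response, PFS, OS"; then "Toxicity details (type of toxicity, grade". The toxicity item names no line or regimen.
- **What the endpoint needs.** Study Endpoints counts ORR as confirmed complete or partial response by RECIST v1.1 "after initiation of immune checkpoint inhibitors treatment". PFS runs from the first dose of study treatment. The exploratory adverse-event endpoint concerns events in response to checkpoint inhibitors. OS runs from diagnosis.
- **Prospective population.** Patients have had no prior treatment for advanced disease. They receive IO as first line for metastatic disease or as consolidation for locally advanced disease (prospective inclusion criteria 6 and 8).

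**The concern.** The response item is tied to a line of therapy, whereas the cohort and the endpoint are tied to a drug class. The two agree only when IO was given first line. The protocol itself leads one to expect retrospective patients for whom it was not. Background and Rationale says of the monotherapy approvals that pembrolizumab was approved in first and second line, "whereas nivolumab and atezolizumab only in second line". Retrospective criterion 6 admits patients with driver alterations who had an IO line, and the Background names targeted drugs as the treatment of choice for that group.

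What is at stake is an outcome label. Predicting response to checkpoint inhibitors is the overall primary objective. The retrospective data build the R-Model and the first version of the physician decision tool, and the prospective data then feed models learned on them. If response to the IO line is not collected, no later analysis decision can recover it without going back to the charts.

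**Working it through.** The protocol states no figure on this point, so there is none to reproduce. The check follows each type of patient through the row as written and asks whether the ORR endpoint can be derived.

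| Patient | Regimen options offered under first line | Does the best-response item give response after IO start? |
|---|---|---|
| Prospective, first-line IO | Fit | Yes |
| Retrospective, IO in first line | Fit | Yes |
| Retrospective, platinum first, nivolumab second | None fits the platinum line | Not if read literally |
| Retrospective, driver alteration, targeted drug first, IO later | None fits the targeted line | Not if read literally |
| IO as consolidation or maintenance in locally advanced disease (retrospective criterion 3, prospective criterion 8) | Unclear whether first line means the preceding treatment or the IO | Unclear |

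For the third and fourth rows a site has three possible entries:

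1. Record the response to the earlier regimen. The label is then not the ORR of Study Endpoints. The order in time is also reversed: the table takes symptoms, weight loss and the neutrophil/lymphocyte ratio at the start of IO, so the outcome would precede its predictors.
2. Enter the later IO line as if it were first line. The response label is then right, but the recorded line of therapy is wrong.
3. Leave the item blank. The response label is missing.

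Six centres contribute retrospective data and may choose differently. Nothing listed in the row would show which choice was made.

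The other outcome items in the row:

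- Duration of response and PFS follow the first-line response item with no anchor of their own. Study Endpoints anchors PFS to study treatment, so the row needs to say the same.
- Toxicity has no anchor in the row, but the adverse-event endpoint supplies one. This is an ambiguity and not a wrong assignment.
- OS is counted from diagnosis and is not affected by the line named in the row.

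Size: if a share f of the retrospective cohort received IO after first line, the number affected is 2000 × f. The protocol does not give f. Each 10 percentage points is 2000 × 0.10 = 200 patients.

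**The case against.** The best defence is that first line is loose wording for the IO line. The row gives platinum response its own item and offers only IO regimens under first line. Read as a whole, it already separates earlier response as a predictor from IO response as the outcome. Study Endpoints anchors ORR and adverse events to checkpoint inhibitors. Retrospective patients without minimal treatment information, such as IO start and stop dates, are excluded, so sites must know when IO began. The row is also a summary; data entry is left to the CRF and the Data Management Plan, which are not shown and may define the field properly.

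Much of this stands. A reader might infer that later-line patients are in fact given response and toxicity labels from a pre-IO regimen. The protocol does not say so. It is one of three possible outcomes for response, and for toxicity it is not supported at all.

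The defence does not remove the conflict. Elsewhere the same table names the start of immunotherapy when it means it, so a site has reason to take first line literally. Study Endpoints defines the outcome, but the table lists what is collected, and an item for first-line response does not yield response to a second-line drug. The required minimum treatment data give IO dates and agent, not response. The loose reading still makes a site enter a later line under a first-line label.

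**Conclusion.** The point holds for one outcome item in one cohort. For retrospective patients whose IO was not first line, the table as written has no field for best response to IO, and it conflicts with both the cohort definition and the ORR definition. Their response label would be wrong or inconsistent. It is more than missing detail, because the protocol itself fixes the collected variable. The unanchored toxicity item needs only clarification.

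This rests on two things: that such patients are in the cohort, which the any-line criterion allows and the Background makes likely; and that the CRF follows the table, which cannot be checked here.

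A reader might wish to turn this into a loss of AUC and set it against the 0.1 gain on which the study is powered. The protocol does not support that step:

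- The share of later-line patients and the sites' choice among the three entries are both unknown.
- Noise in training labels does not translate by a simple formula into lower AUC against correct labels.
- The 0.1 gain is assessed in the 200 prospective cases, who receive frontline IO.
- The stated success criterion uses 2-year PFS and OS, not best response.

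**What to change.** In the Treatment Characteristics row:

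- Replace first line with *index IO line*, defined as the first IO-containing line.
- Tie regimen, best response, duration of response and PFS to the first dose of that line.
- Keep response to earlier regimens only under the existing item for previous treatments and platinum response, where it serves as a predictor.
- State the same anchor for toxicity, as a clarification in line with Study Endpoints.
- State how the index IO line applies when IO is given as consolidation (prospective criterion 8) or maintenance (retrospective criterion 3).

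The cost is the wording of one table row and the matching CRF labels. Sites read the same charts. Retrospective patients already entered whose IO came after first line need these fields re-checked before the labels are used to train the R-Model. For prospective patients with first-line IO for metastatic disease the content does not change; for those with consolidation IO it depends on the definition adopted.
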